#### **Data Quality Assurance**

All subject data relating to the study will be recorded on printed or electronic CRF unless transmitted to the sponsor or designee electronically (eg, laboratory data, centrally or adjudicated data). The investigator is responsible for verifying that data entries are accurate and correct by physically or electronically signing the CRF.

The investigator must maintain accurate documentation (source data) that supports the information entered in the CRF.

The investigator must permit study-related monitoring, audits, IRB/IEC review, and regulatory agency inspections and provide direct access to source data documents.

The sponsor or designee is responsible for the data management of this study including quality checking of the data.

Clinical monitors will perform ongoing source data verification to confirm that data entered into the CRF by authorized site personnel are accurate, complete, and verifiable from source documents; that the safety and rights of subjects are being protected; and that the study is being conducted in accordance with the currently approved protocol and any other study agreements, ICH GCP, and all applicable regulatory requirements per the sponsor's monitoring plan.

The investigator agrees to cooperate with the clinical monitor to ensure that any problems detected in the course of these monitoring visits, including delays in completing CRFs, are resolved.

The Amgen representative(s) and regulatory authority inspectors are responsible for contacting and visiting the investigator for the purpose of inspecting the facilities and, upon request, inspecting the various records of the clinical study (eg, CRFs and other pertinent data) provided that subject confidentiality is respected.

In accordance with ICH GCP and the sponsor's audit plans, this study may be selected for audit by representatives from Amgen's Global Research & Development Compliance and Audit function (or designees). Inspection of site facilities (eg, pharmacy, protocol-required therapy storage areas, laboratories) and review of study-related

records will occur to evaluate the study conduct and compliance with the protocol, ICH GCP, and applicable regulatory requirements.

Retention of study documents will be governed by the Clinical Trial Agreement.

CRFs must be completed in English. TRADENAMES® (if used) for concomitant medications may be entered in the local language. Consult the country-specific language requirements.

All written information and other material to be used by subjects and investigative staff must use vocabulary and language that are clearly understood.

### **Source Documents**

The investigator is to maintain a list of appropriately qualified persons to whom he/she has delegated study duties. All persons authorized to make entries and/or corrections on CRFs will be included on the Amgen Delegation of Authority Form.

Source documents provide evidence for the existence of the subject and substantiate the integrity of the data collected. Source documents are filed at the investigator's site.

Source documents are original documents, data, and records from which the subject's CRF data are obtained. These include but are not limited to hospital records, clinical and office charts, laboratory and pharmacy records, diaries, microfiches, radiographs, and correspondence. Source documents may also include data captured in the Interactive Voice Response System (IVRS)/Interactive Web Response System (IXRS) system (if used, such as subject ID and randomization number) and CRF entries if the CRF is the site of the original recording (ie, there is no other written or electronic record of data, such as [REDACTED]

Data reported on the CRF or entered in the electronic CRF that are transcribed from source documents must be consistent with the source documents or the discrepancies must be explained. The investigator may need to request previous medical records or transfer records, depending on the study. Also, current medical records must be available.

The Investigator and study staff are responsible for maintaining a comprehensive and centralized filing system of all study-related (essential) documentation, suitable for inspection at any time by representatives from Amgen and/or applicable regulatory authorities.

Elements to include:

- Subject files containing completed CRFs, informed consent forms, and subject identification list
- Study files containing the protocol with all amendments, Investigator's Brochure, copies of prestudy documentation, and all correspondence to and from the IRB/IEC and Amgen
- Investigational product-related correspondence including Proof of Receipts (POR), Investigational Product Accountability Record(s), Return of Investigational Product for Destruction Form(s), Final Investigational Product Reconciliation Statement, as applicable
- Non-investigational product(s), and/or medical device(s) or combination product(s) documentation, as applicable

Retention of study documents will be governed by the Clinical Trial Agreement.

### **Study and Site Closure**

Amgen or its designee may stop the study or study site participation in the study for medical, safety, regulatory, administrative, or other reasons consistent with applicable laws, regulations, and GCP.

Both Amgen and the Investigator reserve the right to terminate the Investigator's participation in the study according to the Clinical Trial Agreement. The investigator is to notify the IRB/IEC in writing of the study's completion or early termination and send a copy of the notification to Amgen.

Subjects may be eligible for continued treatment with Amgen investigational product(s) by an extension protocol or as provided for by the local country's regulatory mechanism. However, Amgen reserves the unilateral right, at its sole discretion, to determine whether to supply Amgen investigational product(s) and by what mechanism, after termination of the study and before the product(s) is/are available commercially.

### **Compensation**

Any arrangements for compensation to subjects for injury or illness that arises in the study are described in the Compensation for Injury section of the Informed Consent that is available as a separate document.

## 12.4 Appendix 4. Safety Events: Definitions and Procedures for Recording, Evaluating, Follow-up and Reporting

### Definition of Adverse Event

Adverse Event Definition

An adverse event is any untoward medical occurrence in a clinical study subject irrespective of a causal relationship with the study treatment.

Note: An adverse event can therefore be any unfavorable and unintended sign (including an abnormal laboratory finding), symptom, or disease (new or exacerbated) temporally associated with the use of a treatment, combination product, medical device or procedure.

Note: Treatment-emergent adverse events will be defined in the Statistical Analysis Plan (SAP).

Events Meeting the Adverse Event Definition


Any abnormal laboratory test results (hematology, clinical chemistry) or other safety assessments (eg, electrocardiogram [ECG], radiological scans, vital signs measurements), including those that worsen from baseline, that are considered clinically significant in the medical and scientific judgment of the investigator (ie, not related to progression of underlying disease).

Exacerbation of a chronic or intermittent pre-existing condition including either an increase in frequency and/or intensity of the condition.

New conditions detected or diagnosed after study treatment administration even though it may have been present before the start of the study.

Signs, symptoms, or the clinical sequelae of a suspected drug-drug interaction.

Signs, symptoms, or the clinical sequelae of a suspected overdose of either study treatment or a concomitant medication. Overdose per se will not be reported as an adverse event/serious adverse event unless it is an intentional overdose taken with possible suicidal/self-harming intent. Such overdoses are to be reported regardless of sequelae.

For situations when an adverse event or serious adverse event is due to primary tumor type being studied report all known signs and symptoms. Death due to disease progression in the absence of signs and symptoms should be reported as the primary tumor type (eg, metastatic pancreatic cancer). Note: The term "disease progression" should not be used to describe the adverse event.

The signs, symptoms, and/or clinical sequelae resulting from lack of efficacy will be reported as adverse event or serious adverse event if they fulfill the definition of an adverse event or serious adverse event. Also, "lack of efficacy" or "failure of expected pharmacological action" also constitutes an adverse event or serious adverse event.

Events NOT Meeting the Adverse Event Definition

Medical or surgical procedure (eg, endoscopy, appendectomy): the condition that leads to the procedure is the adverse event.

Situations in which an untoward medical occurrence did not occur (social and/or convenience admission to a hospital).

Anticipated day-to-day fluctuations of pre-existing disease(s) or condition(s) present or detected at the start of the study that do not worsen.

### Definition of Serious Adverse Event

**A Serious Adverse Event is defined as any untoward medical occurrence that, meets at least 1 of the following serious criteria:**

#### **Results in death (fatal)**

##### **Immediately life-threatening**

The term "life-threatening" in the definition of "serious" refers to an event in which the subject was at risk of death at the time of the event. It does not refer to an event, which hypothetically might have caused death, if it were more severe.

#### **Requires in-patient hospitalization or prolongation of existing hospitalization**

In general, hospitalization signifies that the subject has been detained (usually involving at least an overnight stay) at the hospital or emergency ward for observation and/or treatment that would not have been appropriate in the physician's office or outpatient setting. Complications that occur during hospitalization are an adverse event. If a complication prolongs hospitalization or fulfills any other serious criteria, the event is serious. When in doubt as to whether "hospitalization" occurred or was necessary, the adverse event is to be considered serious.

Hospitalization for elective treatment of a pre-existing condition that did not worsen from baseline is not considered an adverse event.

#### **Results in persistent or significant disability/incapacity**

The term disability means a substantial disruption of a person's ability to conduct normal life functions.

This definition is not intended to include experiences of relatively minor medical significance such as uncomplicated headache, nausea, vomiting, diarrhea, influenza, and accidental trauma (eg, sprained ankle) which may interfere with or prevent everyday life functions but do not constitute a substantial disruption.

#### **Is a congenital anomaly/birth defect**

#### **Other medically important serious event**

Medical or scientific judgment is to be exercised in deciding whether serious adverse event reporting is appropriate in other situations such as important medical events that may not be immediately life-threatening or result in death or hospitalization but may jeopardize the subject or may require medical or surgical intervention to prevent 1 of the other outcomes listed in the above definition. These events are typically to be considered serious.

Examples of such events include invasive or malignant cancers, intensive treatment in an emergency room or at home for allergic bronchospasm, blood dyscrasias or convulsions that do not result in hospitalization, or development of drug dependency or drug abuse.

### Recording Adverse Events and Serious Adverse Events

#### **Adverse Event and Serious Adverse Event Recording**

- When an adverse event or serious adverse event occurs, it is the responsibility of the investigator to review all documentation (eg, hospital progress notes, laboratory, and diagnostics reports) related to the event.
- The investigator will then record all relevant adverse event/serious adverse event information in the Event case report form (CRF).

- The investigator must assign the following adverse event attributes:
  - Adverse event diagnosis or syndrome(s), if known (if not known, signs or symptoms);
  - Dates of onset and resolution (if resolved);
  - **Did the event start prior to the first dose of investigational product;**
  - **Assessment of seriousness;**
  - Severity (or toxicity defined below);
  - Assessment of relatedness to Amgen investigational product (romiplostim or placebo) or other protocol-required therapies; mandated study activity/procedure;
  - Action taken; and
  - **Outcome of event.**
- If the severity of an adverse event changes from the date of onset to the date of resolution, record as a single event with the worst severity on the Event CRF.
- It is not acceptable for the investigator to send photocopies of the subject's medical records to Amgen in lieu of completion of the Event CRF page.
- If specifically requested, the investigator may need to provide additional follow-up information, such as discharge summaries, medical records, or extracts from the medical records. In this case, all subject identifiers, with the exception of the subject number, will be blinded on the copies of the medical records before submission to Amgen.
- The investigator will attempt to establish a diagnosis of the event based on signs, symptoms, and/or other clinical information. In such cases, the diagnosis (not the individual signs/symptoms) will be documented as the adverse event/serious adverse event.

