##### 9.2.3.1.1.2 Serious Adverse Events

The investigator is responsible for ensuring that all serious adverse events observed by the investigator or reported by the subject that occur after signing of the informed consent through the end of study are reported using the Event CRF.

All serious adverse events will be collected, recorded and reported to the sponsor or designee within 24 hours, as indicated in [Appendix 4](#). The investigator will submit any updated serious adverse event data to the sponsor within 24 hours of it being available.

The criteria for grade 4 in the CTCAE version 5.0 grading scale differs from the regulatory criteria for serious adverse events. It is left to the investigator's judgment to report these grade 4 abnormalities as serious adverse events. **For any adverse event that applies to this situation, comprehensive documentation of the event's severity must be recorded in the subject medical records.**

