#### Types of Events to be reported on this form

- Serious Adverse Events (regardless of causal relationship to IP)

1. Site Information  
Site Number\* – Enter your assigned site number for this study  
Investigator\*, Country\*, Reporter\*, Phone No., and Fax No. – Enter information requested

2. Subject Information  
Subject ID Number\* – Enter the entire number assigned to the subject  
Age at event onset, Sex, and Race – Enter the subject's demographic information  
End of Study date – If the subject has already completed the study or terminated the study early, enter the End of Study date

*If you are submitting follow-up information to a previous report, provide the serious adverse event term for the previous report as well as the start date for the initial event.*

3. Serious Adverse Event

Provide the date the Investigator became aware of this information

Serious Adverse Event Diagnosis or Syndrome\* –  
➤ If the diagnosis is known, it should be entered. Do not list all signs/symptoms if they are included in the diagnosis.  
➤ If a diagnosis is not known, the relevant signs/symptoms should be entered.  
➤ If the event is fatal, the cause of death should be entered and autopsy results should be submitted, when available.

Date Started\* – Enter date the adverse event first started (not the date on which the event met serious criteria) rather than the date of diagnosis or hospitalization. This is a mandatory field.

Date Ended – Enter date the adverse event ended and not the date when the event no longer met serious criteria. If the event has not ended at the time of the initial report, a follow-up report should be completed when the end date is known. If the event is fatal, enter the date of death as the end date.

If event occurred before the first dose of Investigational Product (IP)/drug under study, add a check mark in the corresponding box.

Is event serious?\* – Indicate Yes or No. This is a mandatory field.

Serious Criteria Code\* – This is a mandatory field for serious events. Enter all reasons why the reported event has met serious criteria:

- Immediately life-threatening – Use only if the subject was at immediate risk of death from the event as it occurred. Emergency treatment is often required to sustain life in this situation.

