Events categorized as AEs starting on or after first dose of investigational product as determined by “Did event start before first dose of investigational product” equal to “No” or missing on the Events eCRF; and up to and including 30 days after the last dose of investigational product (excluding events reported after End of Study date).

Any event which has started 30 days after the last dose of IP (i.e., during LTFU period) will not be considered as TEAE.

[figure not shown]
6. Analysis Sets

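### The TEAE definition has no clause for worsening, so a serious or procedure-related event recorded in screening that worsens on investigational product is left out of the TEAE tables

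*Protocol*

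**What the plan says.** **Recording.** Appendix 4 (Protocol 12.4) covers an adverse event whose severity changes between onset and resolution with one instruction: "from the date of onset to the date of resolution, record as a single event with the worst severity on the Event CRF". The attributes the investigator must assign include onset and resolution dates and the item "Did the event start prior to the first dose of investigational product". A date of worsening is not among them.

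**When recording begins.** Protocol 9.2.3.1.1.2 applies to all serious adverse events "that occur after signing of the informed consent through the end of study are reported using the Event CRF". Under 9.2.3.1.1.1 and the Schedule of Activities footnotes, non-serious events possibly related to a study procedure are also recorded from consent. All other non-serious events are recorded only once dosing has begun. Screening lasts up to 28 days.

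**Classification.** Appendix 4 leaves the definition of a treatment-emergent adverse event (TEAE) to the SAP. SAP Section 5 defines TEAEs as "Events categorized as AEs starting on or after first dose of investigational product as determined by" the CRF item on start before first dose. The answer must be No "or missing on the Events eCRF; and up to and including 30 days after the last dose of investigational product".

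**Tables.** SAP 9.6.1 plans subject incidence by system organ class and preferred term for all TEAEs, serious TEAEs, those of grade 3 or higher, fatal TEAEs and several other TEAE categories. Its sentence on events of interest does not repeat the TEAE restriction, but Protocol 10.3.2.3.1 places events of interest within the TEAE summary.

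**The concern.** Each rule is ordinary on its own. The difficulty is the combination. The single-record rule folds a later, worse grade into the record of an event that began earlier. The TEAE rule then sorts that record by its start alone. A grade reached on treatment is therefore filed under a pre-treatment onset, and no recorded date allows it to be recovered.

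The safety assessment rests mainly on comparing TEAE incidence between arms. Protocol 3.3.3.2 names thrombotic and thromboembolic complications as a key risk, and subjects enter with active cancer and low platelet counts after recent chemotherapy. With 162 subjects randomized 2:1, one or two severe events in or out of a table can alter how it reads.

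**Working it through.** No arithmetic applies, and the plan states no figure to reproduce. The check follows different kinds of event that begin before first dose and worsen on treatment through the recording and classification rules.

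1. **Serious event begun in screening.** It is recorded from consent. If it rises in grade or becomes fatal on investigational product, Appendix 4 keeps one record at the worst grade with the first onset date. The item on start before first dose is Yes, so it is not a TEAE under SAP Section 5 and is absent from the TEAE tables.
2. **Procedure-related non-serious event begun in screening.** It is also recorded from consent. If it rises in grade or becomes serious on treatment, the result is the same.
3. **Any other non-serious event begun in screening.** It is not reportable before first dose, so normally no record exists. If its worsening is entered as a new event, it is a TEAE. If the site dates it back to first onset, it is not. The documents do not settle which.
4. **Chronic or intermittent condition present before consent.** Appendix 4 treats an increase in its frequency or intensity as an adverse event in its own right. Onset is then after dosing, and the event is a TEAE.
5. **Any of these with the CRF item blank.** A missing answer counts towards TEAE status.

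The gap is therefore definite in cases 1 and 2, open in case 3 and absent in case 4.

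Two other provisions might have closed cases 1 and 2:

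- *The exacerbation and new-detection rules in Appendix 4.* The first concerns chronic or intermittent pre-existing conditions, and an acute bleed or clot arising in screening is not clearly either. The second cannot apply to an event already on record.
- *Medical history (Protocol 9.2.1.3).* It stops at consent, so it does not cover the interval between consent and first dose.

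The completion instruction for the paper serious-event form in Figure 12-1 points the same way on dating: "Enter date the adverse event first started (not the date on which the event met serious criteria) rather than the date of diagnosis or hospitalization".

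Outside the TEAE tables, these events remain visible in four places:

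- the listing of all adverse events (SAP 9.6.1);
- for deaths, the survival analysis and the cause-of-death summary by arm (SAP 9.5.2.4);
- for selected analytes, the shift tables from baseline to worst value (SAP 9.6.2);
- the DMC's review of all available safety data (SAP 9.6.1).

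None of the planned summaries among these tabulates, by arm and grade, a non-fatal clinical event such as a clot or bleed that worsened on treatment.

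**The case against.** The strongest reply is that the affected class is narrow. Most non-serious screening events have no pre-dose record, Appendix 4 already gives some worsening its own event, and a blank item defaults to TEAE. This stands, and it limits the point to serious and procedure-related events recorded before first dose.

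Eligibility narrows it further. Exclusion criteria 209 and 210 bar recent venous and arterial thrombosis, criterion 211 bars recent active infection, and criterion 227 lets the investigator exclude for other risks. A subject with a serious event in screening may well be a screen failure. This lowers the expected number but does not close the gap: the windows in 209 and 210 are counted back from screening, and 209 admits some subjects with a new thrombotic event who are anticoagulated and stable. A clot arising during screening is not barred in every case.

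Figure 12-1 is a paper form for when electronic capture is unavailable, and the completion guideline for the ordinary Event CRF is not among the documents. That is fair, so the form is only supporting evidence. The conclusion needs only the single-record rule, the start-before-dose item and the SAP definition.

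A reader might infer that the rule hides romiplostim harm in particular, or that such events would surface only in listings. The documents support neither inference. The rule applies equally to both blinded arms, and deaths, selected laboratory changes and DMC review are handled without regard to TEAE status.

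**Conclusion.** The point holds for serious and procedure-related adverse events that begin between consent and first dose and then increase in grade, become serious or become fatal on investigational product. By the stated rules they are left out of the TEAE incidence tables in either arm. This is a classification error built into the definition, and the recorded data give no date from which to correct it later.

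The size cannot be derived. The documents give no rate of serious events in screening and no probability of worsening. Because the exposed window is at most 28 days and eligibility removes some subjects, the number is probably small. It is tempting to assume rates and set the result against the thromboembolic rate in the cited phase 2 study (4 of 32). That would compare events of all kinds in both arms with clots in the romiplostim arm, so no percentage loss of signal can be claimed.

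The conclusion assumes that sites apply the single-record rule as written to events begun before dosing, and that no CRF guideline outside these documents says otherwise.

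**What to change.** - **SAP Section 5.** Define a TEAE as an adverse event that starts on or after first dose of investigational product, or that starts earlier and increases in grade or becomes serious on or after first dose, in both cases up to 30 days after last dose. A fatal outcome is covered, since it is a serious criterion in Appendix 4.
- **Appendix 4 and CRF completion instruction.** For an event begun before first dose that worsens afterwards, open a new Event record dated at the worsening, or capture that date on the existing record.
- **Appendix 4, internal consistency.** Reconcile the single-record rule with the rule that an exacerbation is an adverse event, so that sites have one instruction for worsening of a pre-dose event.
- **Data already collected.** Query the records flagged as starting before first dose for any later increase in grade or seriousness and its date, before unblinding.

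The cost is a further SAP version after 4.0, a recording instruction, a limited set of queries and a few extra records, which will raise event counts slightly. No endpoint, sample size or efficacy analysis changes.
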